### Phase 1-3: Quantitative Data Analysis

To address research objectives #1 and #2, we will divide the patients (and FMs) into three groups:

- a. Pre-COVID: Deaths that occurred in an acute care hospital before the impact of the pandemic was first felt in Ottawa (November 1st, 2019–February 29th, 2020): approximately 160 patients.
- b. COVID: Deaths that occurred in an acute care hospital due to COVID-19 (March 1st – August 31st, 2020). Approximately 250 COVID-19 deaths have been reported between January and June 2019 in Ottawa by Ottawa Public Health, of which preliminary data suggest approximately 80 patients died in acute care.
- c. Non-COVID: Deaths that occurred in an acute care hospital between March 1st – August 31st, 2020 but were not COVID-19 related: approximately 160 patients.

To assess the overall impact of the pandemic, we will perform statistical comparisons of clinical and end-of-life care metrics for the Pre-COVID vs. COVID and Non-COVID groups combined. Patients will be matched based on their health and demographic profiles in a 2:1:2 ratio (2 decedents in pre-COVID period: 1 decedent during the pandemic who died of COVID-19: 2 decedents who died during the pandemic of non-COVID-19 causes). We will compare the COVID vs. Non-COVID groups to determine how much of the impact was specifically associated with COVID infection as opposed to the pandemic in general. Pairwise comparisons will be performed using an unpaired t-test or Mann-Whitney test as appropriate for the distribution of the data. We will then also use logistic regression analysis to identify factors associated with an ICG score  $>25$  (i.e. severe scores).

To address research objective #3, we will compare the changes in ICG scores between baseline and 6-months post-baseline for FMs who did versus did not participate in the VSGs (i.e. the difference in differences). This comparison is important since grief symptoms typically improve over time even without intervention. In addition, group allocation is not random and so our analysis may be

confounded by the possibility that people who choose to participate in support groups have more severe symptoms. We will therefore perform an adjusted analysis similar to Newsom et al. in their naturalistic controlled trial of community-based bereavement support. We will estimate an average score for the outcome variable at each time point for the support-group and no-support-group (control) conditions. Where baseline differences in clinical, demographic or loss-related variables exist, these variables will be added as covariates. Assumptions of linearity, multicollinearity, homoscedasticity, and normality of residuals will be tested prior to analysis.

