## Abstract

**Background:** Severe grief reactions (SGR), or complicated grief, are experienced by 2-3% of the population after the loss of a loved one, and can be associated with declining health, social distress, increased use of healthcare resources and higher mortality. SGR can be related to the circumstances of the patient at the end of life, particularly in deaths that were unexpected or traumatic, when the family member was unprepared or unsupported. The COVID-19 pandemic has affected many aspects of end-of-life care. For example, infection control measures may reduce interactions between long-term care residents and family members, and have often limited in-person family visiting to the final hours of life, or no visiting at all for patients with COVID-19. Anecdotally, this disruption of normal interactions has been difficult for patients and families alike, and we know that isolation and lack of closure with a loved one can contribute to the risk of SGR. The prevalence of SGR is expected to rise amid increased challenges in supporting a surge of people with SGR due to physical distancing and limited bereavement resources.

**Methods:** The proposed mixed methods explanatory study includes both retrospective and prospective data collection. The quantitative components will principally consist of natural experiments to identify patient/FM characteristics indicating a high risk of SGR during the COVID-19 pandemic. The qualitative components will deepen our understanding of the impact of COVID-19 on bereavement, while providing formative evaluation for the virtual support groups. Study subjects will include all patients who died in an acute care facility in Ottawa (The Ottawa Hospital, Queensway-Carleton Hospital, and Hôpital Montfort) from November 11, 2019 until August 31, 2020, and their primary contact (as indicated in their medical record).

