### Study Setting

Study subjects will include all patients who died in an acute care facility in Ottawa (The Ottawa Hospital, Queensway-Carleton Hospital, and Hôpital Montfort) from November 1st, 2019 to August 31st, 2020, and their contacts (as indicated in their medical record). The Virtual support groups will be organized by Bereaved Families of Ontario – Ottawa through a virtual platform.

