### Study Participants

We will collect retrospective data from approximately 550 deceased patients. We plan to recruit approximately 200 FMs for the prospective portion of the study with an expected 100 FMs participating in the VSG and 20 FMs in the qualitative interviews. Note that family members will participate in the virtual support group as part of routine care available to them – the support group is not a study-specific intervention, nor will any research team members be involved in the administration of the virtual support group. The scope of the research study related to the virtual support group is to a) inform the 200 bereaved family participants about the support group, so that they may seek out this care available to them and b) conduct qualitative interviews with 20 participants who attended the virtual support group. As such, while we will obtain consent for conducting the qualitative interviews, consent will not be obtained for participation in the virtual support groups.

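### Decedents are matched 2:1:2 but analysed with unpaired tests, and the pooled pandemic contrast carries a 1:2 COVID mix set by the matching ratio

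*Combined protocol and SAP*

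**What the plan says.** All of this is in the Combined protocol and SAP, mostly in *Phase 1-3: Quantitative Data Analysis*.

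- **Groups.** Pre-COVID about 160, COVID about 80, Non-COVID about 160. The COVID figure is provisional: "of which preliminary data suggest approximately 80 patients died in acute care".
- **Selection.** "Patients will be matched based on their health and demographic profiles in a 2:1:2 ratio". The text does not say whether this means individual matched sets or frequency matching.
- **Overall effect of the pandemic.** "we will perform statistical comparisons of clinical and end-of-life care metrics for the Pre-COVID vs. COVID and Non-COVID groups combined".
- **Second named contrast.** COVID against Non-COVID, "to determine how much of the impact was specifically associated with COVID infection as opposed to the pandemic in general".
- **Tests.** "Pairwise comparisons will be performed using an unpaired t-test or Mann-Whitney test as appropriate for the distribution of the data". For Objectives #1 and #2, regression is named only for an ICG score above 25. The covariate adjustment at the end of the section belongs to the support-group comparison (Objective #3). *Data Collection* mentions regression models without tying them to these metrics.
- **Population.** *Study Setting* says "Study subjects will include all patients who died in an acute care facility in Ottawa", and *Phase 1: Retrospective chart review* says the same of the records to be abstracted. *Study Participants* says "We will collect retrospective data from approximately 550 deceased patients".

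**The concern.** Matching is a design feature that the analysis should reflect. Here it enters the selection of patients and then disappears: an unpaired test treats the 400 decedents as independent and unmatched. If matching is by set and works, the precision it buys is not used.

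The second issue is what the pooled contrast estimates. Its COVID component has a weight of one third because the investigators take one COVID death for every two Non-COVID deaths in the pandemic period. The plan itself gives reason to expect the two effects to differ. The Abstract describes measures that "limited in-person family visiting to the final hours of life, or no visiting at all for patients with COVID-19", family presence around the time of death is among the abstracted items, and the COVID against Non-COVID contrast exists to separate the two. A figure presented as the overall effect of the pandemic would then describe this matched sample, and not necessarily the hospitals' decedents.

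**Working it through.** **Plan's own figure.** 160/80 : 80/80 : 160/80 = 2:1:2, so the group sizes agree with the ratio. COVID share of the pooled group: 80/(80 + 160) = 1/3. Total: 160 + 80 + 160 = 400.

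**1. Unpaired tests on matched sets.** The plan gives no significance level, effect size or within-set correlation (rho). I assume two-sided 5%, 0.25 SD, and 80 complete sets of 2 Pre-COVID and 3 pandemic decedents.

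- Unpaired SE = sqrt(1/160 + 1/240) = 0.1021 SD.
- True variance under set matching = (1 - rho)(1/2 + 1/3)/80, which is (1 - rho) times the unpaired variance.
- Type I error of the unpaired test = 2[1 - Phi(1.96/sqrt(1 - rho))].
- Unpaired power = Phi[(0.25 - 1.96 x 0.1021)/true SE]. Matched power = Phi[0.25/true SE - 1.96].

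| rho (assumed) | true SE | unpaired SE too large by | type I error, unpaired | power, unpaired | power, matched |
|---|---|---|---|---|---|
| 0.1 | 0.0968 | 5% | 3.9% | 70% | 73% |
| 0.3 | 0.0854 | 20% | 1.9% | 72% | 83% |

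Simulation of the unpaired t-test at rho = 0.3 gave a type I error of 1.8%. A simulated binary metric (assumed 60% against 47.5%) gave 70% unpaired against 73% matched at an intraclass correlation of 0.1, and 73% against 84% at 0.3.

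**2. Pooled contrast.** Let dC and dN be the COVID and Non-COVID effects against Pre-COVID, and w the true COVID share of pandemic-period hospital deaths.

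- Pooled effect in the sample = (80 dC + 160 dN)/240 = dC/3 + 2dN/3.
- Shift from the effect at share w = (1/3 - w)(dC - dN), assuming dN in matched Non-COVID deaths holds for all Non-COVID deaths.

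| w (assumed) | shift toward the COVID effect per 10-point difference |
|---|---|
| 5% | 2.8 points |
| 10% | 2.3 points |
| 20% | 1.3 points |
| 25% | 0.8 points |
| 33.3% | 0 |

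Above one third the shift changes sign. If dC = dN it is zero throughout.

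The plan's counts do not settle w. The periods are 121 days (1 November to 29 February) and 184 days (1 March to 31 August), 305 in all. Taking 80 COVID deaths as final:

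- (a) 160 is every Pre-COVID death and the non-COVID rate is unchanged: 160/121 x 184 = 243; 80/(80 + 243) = 24.7%.
- (b) 550 is every death and the non-COVID rate is constant: (550 - 80) x 184/305 = 284; 80/(80 + 284) = 22.0%.
- (c) 550 is every death and 160 is every Pre-COVID death: 80/(550 - 160) = 20.5%.

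The share reaches one third at 122, 127 and 130 COVID deaths respectively. The count of 80 runs only to June, while the window closes on 31 August.

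**3. Recovering the separate effects.** With D the pooled contrast and E = dC - dN, dN = D - E/3 and dC = D + 2E/3. This works for means and proportions, but not for Mann-Whitney results.

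**The case against.** The strongest reply is that little is hidden and little is wrong. The ratio and group sizes are stated, so the 1:2 mix is open to any reader. With three groups, the reference to pairwise comparisons can reasonably include Pre-COVID against Non-COVID. For means and proportions the separate effects can be worked out in any case. If matching is by frequency there are no sets to pair, and even with sets the loss at rho = 0.1 is 3 points of power. No primary outcome or confirmatory test is declared for these chart metrics. All of this stands, and it limits the point to one of precision, labelling and explicitness.

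Four stronger readings are tempting, and the documents do not support them.

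- **The unpaired tests produce false positives.** With positive within-set correlation the error runs the other way.
- **The pooled figure overstates the pandemic's effect.** The true share is not given. The three scenarios conflict over which counts are complete, and 160 may simply be a quota of 2 x 80. Scenario (c) implies a rise in non-COVID deaths from 160/121 = 1.32 to (390 - 80)/184 = 1.68 per day, for which nothing in the plan gives a basis.
- **Pre-COVID against Non-COVID has been left out.** It is not named, but the wording does not exclude it.
- **The mismatch between 400, 550 and all deaths shows the contrast is wrong.** It is a separate inconsistency. Analysing every death would remove the artificial mix, but also the case-mix control that matching provides.

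What the reply does not answer is that the named tests do not use the matching, under either form of it, and that the pooled label promises more than a 1:2 matched sample can deliver.

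**Conclusion.** The point holds in a limited form and is worth acting on. It is not a threat to validity.

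On the tests, if matching is by individual set and correlation is positive, the planned intervals are too wide and the tests conservative. The cost in power ranges from about 3 points (rho 0.1) to about 11 points (rho 0.3) for a 0.25 SD effect. Both the set structure and rho are assumptions.

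On the pooled contrast, the estimate depends on the sampling ratio whenever the two effects differ and the true COVID share is not one third. As an illustration only, a share of 20-25% would move it about 1 point toward the COVID effect per 10-point difference. The documents support no particular size or direction.

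**What to change.** 1. State whether matching is by individual set or by frequency, and replace the unpaired tests accordingly: a mixed, conditional logistic or GEE model by set, or regression adjusted for the matching factors.
2. Name Pre-COVID against Non-COVID and Pre-COVID against COVID as reported contrasts with confidence intervals, beside COVID against Non-COVID.
3. Label these contrasts, and any pooled estimate that is kept, as applying to the matched sample (for the pooled one, at a 1:2 mix) and not to all hospital decedents. The separate contrasts need this caveat as much as the pooled one, because Non-COVID deaths are also selected by matching.
4. As a separate matter, reconcile the groups totalling about 400 with the figure in *Study Participants* and with the all-deaths wording in *Study Setting* and *Phase 1: Retrospective chart review*.

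**Cost.** Wording, a set identifier if sets exist, and some extra analysis. *Data Collection* already includes age, sex and medical history. The separate contrasts are less precise than the pooled one: sqrt(1/160 + 1/160)/0.1021 = 1.095 and sqrt(1/160 + 1/80)/0.1021 = 1.342, so SEs are 10% and 34% larger. Unpaired power at 0.25 SD with rho = 0 is 61% (Non-COVID) and 44% (COVID), against 69% pooled. Under set matching at rho = 0.3, the matched analysis gives 76% and 59%. Near rho = 0 the loss is not recovered. More contrasts are also reported, so they are better read as estimates with intervals than as additional tests.

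### Decedents are matched 2:1:2 but the named group comparisons ignore the matching, and the retrospective sample is stated in three ways that are not reconciled

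*Combined protocol and SAP*

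**What the plan says.** All references are to the combined protocol and SAP.

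**Matching and tests.** Under Phase 1-3: Quantitative Data Analysis, "we will divide the patients (and FMs) into three groups": Pre-COVID (about 160), COVID ("preliminary data suggest approximately 80 patients died in acute care") and Non-COVID (about 160). The section continues: "Patients will be matched based on their health and demographic profiles in a 2:1:2 ratio". The main contrast is described as "statistical comparisons of clinical and end-of-life care metrics for the Pre-COVID vs. COVID and Non-COVID groups combined", followed by COVID against Non-COVID. For the test: "Pairwise comparisons will be performed using an unpaired t-test or Mann-Whitney test". The matching variables are not listed, and the section does not say whether matching is individual (sets) or by frequency.

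**Other adjustment.** "We will then also use logistic regression analysis to identify factors associated with an ICG score" above 25; its covariates are not given. The same section adds covariates for the comparison of virtual support group attenders with non-attenders (objective 3). Data Collection says that age, sex, gender, dates and medical history are needed for subgroup analyses and regression models. None of this is tied to the matching.

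**Sample.** Study Setting: "Study subjects will include all patients who died in an acute care facility in Ottawa"; Phase 1: Retrospective chart review likewise says that the records of every such patient will be abstracted. Study Participants: "We will collect retrospective data from approximately 550 deceased patients", with a target of about 200 FMs. Phase 2: Prospective Bereavement Data Collection cites 40-50% enrolment in a previous study.

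**The concern.** Matching takes effort, and its return is precision and balance. An unpaired test treats the groups as independent samples, so its standard error still contains the between-set variation that matching has removed from the contrast. The precision is bought and then not used.

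For FMs the issue is balance rather than precision. Only decedents are matched. FMs inherit the grouping, but fewer than half to one half are expected to enrol, so balance among decedents need not survive among the FMs who answer. Objective 1 concerns the bereavement experience of FMs, so this matters for a main aim.

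The sample statements cannot all describe the same set of patients. The choice between 400 and 550 changes the precision of the chart comparisons and decides how much room there is to reach 200 FMs.

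**Working it through.** **1. Retrospective sample.** The plan's figure is about 550.
- Sum of the stated groups: 160 + 80 + 160 = 400. This is exactly 2:1:2, or 80 sets of five. It falls short of 550 by 150 (150/550 = 27%).
- Using all 250 reported COVID-19 deaths instead of 80 gives 160 + 250 + 160 = 570. That does not give 550 either, and it ignores the acute-care restriction.
- Splitting 550 as 2:1:2: 550/5 = 110, so 220:110:220. That needs 30 COVID deaths beyond the stated 80 (30/80 = 38%). The 80 comes from a count to June, while the window runs to 31 August.
- FMs at 40-50% enrolment, one per decedent (assumed): 160-200 from 400, and 220-275 from 550. The target of 200 needs 200/400 = 50%, or 200/550 = 36%.
- Precision for a yes/no metric near 50% (assumed), pooled contrast, 95% half-width = 1.96 x 0.5 x sqrt(1/n1 + 1/n2): 160 vs 240 gives 10.0 points; 220 vs 330 gives 8.5 points.

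**2. Unpaired tests on matched charts.** The documents give no power calculation, alpha or within-set correlation (rho). I assume two-sided 5% and a range of rho. With complete sets, the true variance of the contrast is (1 - rho) times the variance that the unpaired test uses. Hence:
- Type I error = 2 x (1 - Phi(1.96/sqrt(1 - rho)))
- Unpaired power = Phi((2.80 - 1.96)/sqrt(1 - rho))
- Matched power = Phi(2.80/sqrt(1 - rho) - 1.96)

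The difference is set to give 80% power at rho = 0 for 160 vs 240: 2.80 x sqrt(1/160 + 1/240) = 2.80 x 0.102 = 0.286 SD.

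| Assumed rho | Type I error, unpaired | Power, unpaired | Power using sets |
|---|---|---|---|
| 0.05 | 4.4% | 81% | 82% |
| 0.1 | 3.9% | 81% | 84% |
| 0.3 | 1.9% | 84% | 92% |
| 0.5 | 0.6% | 88% | 98% |

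Simulation of 80 sets of 2+1+2 agrees. At rho 0.1, 0.3 and 0.5 the unpaired t-test rejects in 3.9%, 2.1% and 0.6-0.7% of null datasets and Mann-Whitney in 4.0%, 2.0% and 0.7%; a within-set test stays at 4.9-5.3%. If matching is instead by frequency and exactly balanced, the same figures apply with rho replaced by the share of outcome variance that the matching variables explain.

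**3. FM sets after enrolment** (40-50%, independence assumed).
- All five enrol: 0.4^5 = 1.0% and 0.5^5 = 3.1%, that is 0.8 to 2.5 of 80 sets.
- At least one Pre-COVID and one pandemic FM: (1 - 0.6^2)(1 - 0.6^3) = 50% and (1 - 0.5^2)(1 - 0.5^3) = 66%.

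**4. When FM imbalance arises.** Take a matching factor present in half of the decedents in every group (assumed).
- Enrolment is 40% in one group and 50% in another, unrelated to the factor. The share with the factor is 0.4/(0.4 + 0.4) = 50% in the first and 0.5/(0.5 + 0.5) = 50% in the second. There is no imbalance.
- In one comparison arm only, enrolment is 50% with the factor and 40% without. The share there is 0.5/(0.5 + 0.4) = 55.6% against 50%. If the factor shifts the ICG score by 0.5 SD (assumed), the bias is 0.056 x 0.5 = 0.028 SD, against a standard error of sqrt(1/80 + 1/120) = 0.144 SD.

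So the link between enrolment and the factor must differ between groups; unequal enrolment rates alone are not enough. The second case shows the mechanism only and is not an estimate.

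**5. Model for yes/no metrics in sets of five.** A simulation of 80 sets of 2 vs 3 (assumed set SD 1, true odds ratio 2, log 0.69; 2,000 runs) gave a mean log odds ratio of 0.87 (odds ratio about 2.4) with set indicators in ordinary logistic regression, and 0.69 with conditional logistic regression.

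**The case against.** **The chart error is on the safe side and may be small.** This stands. At a correlation of 0.05-0.1 the loss is 1 to 3 power points. The larger losses need correlations of 0.3 or more, for which the documents offer no evidence, and the plan makes no power claim that this breaks. A reader might infer that ignoring the matching produces false positives; with positive within-set correlation it does the opposite.

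**An unadjusted FM comparison is inferred.** The sentence that introduces the contrasts speaks of clinical and end-of-life metrics, and the FM analysis actually named is the logistic regression for ICG above 25, which may include the matching factors. This stands in part: the FMs are placed in the three groups, and the plan does not say that the regression will carry those factors. A reader might infer that no adjustment is planned anywhere, or that the FM results will be biased. The documents support neither: other adjustment is planned, and nothing is known about how enrolment relates to the matching factors in each group.

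**The sample statements may be reconcilable.** Every death, or 550, could be the pool from which 400 are matched, and more COVID deaths may have occurred after June. Several sections speak of contacts in the plural (the Abstract says primary contact), so more than one FM per decedent is possible. A reader might infer that 550 is unattainable or that 200 FMs cannot be reached; neither follows. But no section states the link, and the chart review section says that every record will be abstracted.

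**The pooled contrast.** One could object that it weights COVID 1/3 and Non-COVID 2/3 by design (80/240 and 160/240). COVID against Non-COVID is planned separately, and the pairwise tests may cover Pre-COVID against Non-COVID, so this is at most an optional reporting note.

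**Conclusion.** The point holds in two parts.

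**Sample.** This is the firmer part and needs no assumption: the plan gives every acute-care death, about 550, and groups that sum to 400, without saying how they relate. The effect on the FM target (50% or 36% enrolment needed) assumes one FM per decedent.

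**Matching.** The named chart comparisons do not use it. If the matching factors predict the outcome, the tests are conservative and precision is lost, from negligible to substantial (84% against 92% power at an assumed correlation of 0.3). For FMs, the sets will mostly be incomplete at the cited enrolment, so balance cannot be presumed. Bias is possible only if the link between enrolment and a matching factor differs between groups, and its size is unknown from the documents.

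Neither part invalidates the study. Both should be corrected before analysis.

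**What to change.** 1. List the matching variables and say whether matching is individual or by frequency.
2. Analyse chart metrics accordingly. If individual: a linear model with a set term for continuous metrics, and conditional (or random-intercept) logistic regression for yes/no metrics such as family presence near death, not set indicators in ordinary logistic regression. If by frequency: adjust for the matching variables.
3. Adjust any three-group FM comparison, and the model for ICG above 25, for the matching variables. Report FM enrolment by group and by matching factor; rates by group alone would not reveal the problem.
4. State one matched sample (about 400 as the groups stand). If every death, or 550, is the pool from which it is drawn, say so. If 550 is the matched total, give group counts that sum to it and show that about 110 COVID deaths are available.
5. State how many decedents' contacts will be approached, and how many per decedent, to reach 200 FMs.
6. Optionally, describe the pooled estimate as a 1/3:2/3 design-weighted average.

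The cost is wording plus modest analysis work; age, sex, gender and medical history are already collected. If 400 is the answer, the stated sample is smaller, the interval is about +/-10.0 rather than +/-8.5 points (yes/no metric near 50%, assumed), and with one FM per decedent the target of 200 sits at the top of the cited enrolment range.

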### Phase 1: Retrospective chart review

We will abstract clinical information from the medical records of all patients who died in an acute care hospital in Ottawa from November 1st, 2019 to August 31st, 2020.

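### The 2:1:2 matching removes none, or only part, of any imbalance between the groups, depending on an unstated pool size, and the Objective #1 contrasts that follow are specified as unadjusted tests

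*Combined protocol and SAP*

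**What the plan says.** All references are to the combined protocol and SAP.

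- **Phase 1-3: Quantitative Data Analysis** defines three groups by date of death and, during the pandemic, by cause. Pre-COVID (November 2019 to February 2020) is put at "approximately 160 patients". For COVID (March to August 2020), "preliminary data suggest approximately 80 patients died in acute care". Non-COVID (the same six months) is again put at about 160.
- The same section then says: "Patients will be matched based on their health and demographic profiles in a 2:1:2 ratio". It spells the ratio out as "2 decedents in pre-COVID period: 1 decedent during the pandemic who died of COVID-19: 2 decedents who died during the pandemic of non-COVID-19 causes". It names no matching variables beyond health and demographic profile, and no algorithm, caliper or balance check.
- Pre-COVID is compared with the two pandemic groups combined, for the overall impact of the pandemic. A second contrast is meant to isolate infection: "We will compare the COVID vs. Non-COVID groups to determine how much of the impact was specifically associated with COVID infection". The tests are an unpaired t-test or a Mann-Whitney test. Logistic regression is specified only for an ICG score above 25. The covariate adjustment described at the end of the section belongs to Objective #3 (support-group participants versus non-participants).
- **Study Participants** gives a different total: "We will collect retrospective data from approximately 550 deceased patients".
- **Phase 1: Retrospective chart review** gives the source population without a count: "We will abstract clinical information from the medical records of all patients who died in an acute care hospital in Ottawa".
- **Data Collection** lists age, sex, comorbidities and admitting source among the abstracted items, and says certain variables are needed for subgroup analyses and regression models.

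**The concern.** Matching changes the balance between groups only by leaving dissimilar candidates out. How much it can do depends on how many more candidates there are than places. The plan does not give that number, and on its printed group sizes the surplus is zero.

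This matters because matching is the only confounding control that the analysis section specifies for the Objective #1 comparisons of clinical and end-of-life metrics. The tests that follow carry no covariates. COVID and other decedents may well differ in age, comorbidity and admitting source, and each of these could affect resuscitative measures, comfort medication, palliative care involvement or family presence. Any difference that matching leaves in place goes directly into a result to be read as the effect of COVID infection or of the pandemic. With no balance check planned, the reader could not see how much was left.

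**Working it through.** **1. The plan's own figures.** Inputs: COVID group about 80, ratio 2:1:2, comparison groups about 160 each.

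- Needed per comparison group: 2 × 80 = 160, which reproduces both printed sizes exactly.
- Total: 160 + 80 + 160 = 400. This does not reproduce 550; the gap is 150.

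**2. Reading A: the 160s are the available deaths.** Surplus = 160 − 160 = 0. Every candidate is used, so each group mean is the same before and after matching. The count has no slack. With 85 or 90 COVID deaths there is a shortfall of 10 or 20 per group; with 70 there are 20 to spare. The 80 rests on preliminary data for deaths reported from January to June, while the COVID window runs to August 31, so the final number may differ.

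**3. Reading B: the 160s are matched targets from a larger pool.** The only larger figure in the documents is 550.

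- Candidates outside the COVID group: 550 − 80 = 470, for 320 places, or 470/320 = 1.47 per place.
- Split evenly (assumption): 235 per group.
- Split by length of window, 4 and 6 months (assumption): 470 × 4/10 = 188 Pre-COVID and 470 × 6/10 = 282 Non-COVID.
- 640 per group is added as an arbitrary large pool; the documents give no such count.

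**4. How much imbalance matching removes.** Optimal 1:2 matching of 80 COVID decedents was simulated on three independent normal factors, each 0.5 SD apart. These settings are assumptions, not document figures.

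The effect on a test was then illustrated for COVID (80) versus Non-COVID (160) on a binary metric with 50% prevalence, each factor worth 5 percentage points per SD and all acting in the same direction (assumptions):

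- SE = √(0.25/80 + 0.25/160) = 0.068
- Bias with nothing removed = 3 × 0.5 × 0.05 = 0.075
- False-positive rate at two-sided 5% = P(|N(bias/SE, 1)| > 1.96)

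| Pool per comparison group | Imbalance removed | Remaining bias | False-positive rate |
|---|---|---|---|
| 160 | 0% | 0.075 | 19.5% |
| 235 | about 48% | 0.075 × 0.52 = 0.039 | about 9% |
| 282 | about 63% | 0.075 × 0.37 = 0.028 | about 7% |
| 640 | about 86% | 0.075 × 0.14 = 0.011 | about 5% |

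**5. Sensitivity.** With 3 points per SD instead of 5, the zero-surplus bias is 3 × 0.5 × 0.03 = 0.045 and the rate is about 10%. If one of three 5-point factors opposes the other two, the net bias is 0.025 and the rate is 6.5% even with zero surplus.

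**6. Precision if 550 are abstracted and all are used.** For Pre-COVID versus pandemic, compare √(1/n₁ + 1/n₂) with its value at 160 versus 240, which is 0.102.

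- Even split, 235 versus 315: 0.086, ratio 0.84, an interval about 16% narrower.
- Split by months, 188 versus 362: ratio 0.88, about 12% narrower.

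**The case against.** A reader might infer that matching has nobody to choose between and therefore cannot balance the groups. The documents do not establish that. The 160s are exactly twice 80, as targets under a 2:1:2 design would be. They are also equal although the windows are 4 and 6 months long: as raw counts they would mean 40 deaths a month before the pandemic and about 27 non-COVID deaths a month during it. The source population is every acute care death in the window, and 550 exceeds 400. Matched targets are at least as plausible as pools.

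A reader might also take 20% as the error rate to expect. It belongs only to the zero-surplus case with assumed, same-direction effects, and it falls quickly as the pool grows. Nor is 550 an established pool: it is the number of charts to be abstracted, and the number of eligible deaths could be larger.

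Finally, one might say that the plan forbids adjustment. It does not. Data Collection anticipates regression models, although the analysis section specifies none for these metrics.

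All of this stands against the stronger reading. It does not remove the point. Under the pool sizes considered, matching leaves between all and about a seventh of the assumed imbalance, the plan gives no means of telling which, and the specified tests do nothing about the remainder.

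**Conclusion.** The concern holds in conditional form. If the printed 160s are the available deaths, 2:1:2 matching around 80 COVID decedents leaves the group means exactly as they were; this is arithmetic and rests on no model. If they are targets from a larger pool, matching removes part of the imbalance, and how much depends on a pool size that the plan does not state. The simulated percentages and error rates indicate scale only: they rest on assumed covariate differences, effects and pool splits.

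On either reading, the Objective #1 contrasts are specified as unadjusted tests after matching of unknown success, and the totals of 400 and 550 are not reconciled. This should be changed. It goes beyond missing detail, because the adjustment is useful whichever reading is right.

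**What to change.** - Estimate Pre-COVID versus pandemic, and COVID versus Non-COVID, by regression or weighting adjusted for age, sex, comorbidities and admitting source, whether or not matching is kept.
- If more than 400 decedents are abstracted, use all of them in these contrasts.
- Report standardised differences for these variables before and after matching, weighting or both.
- State whether 160:80:160 are available deaths or matched targets, give the eligible deaths per group before matching, and reconcile 400 with 550. If matching is kept, name its variables and algorithm.

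The cost is analysis-plan wording and a little more analysis work, with no new data. The drawback is some dependence on the adjustment model. If 550 are abstracted, using them all also narrows the Pre-COVID versus pandemic interval, by about 12% to 16% under the two splits shown.
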